3.4.2. Primary Endpoints

- Primary Performance Outcome: Target vessel patency (patient level) at 12 months

3.4.3. Secondary Endpoints

Secondary performance outcomes

- Reintervention (total and reintervention that can be attributed to branches originally treated with the [REDACTED]) at 12 months and annually through 5 years post-implant
- Target Vessel Technical Success
- Primary Technical Success (Total Endovascular Procedure)
- Target vessel instability at 12 months and annually through 5 years post-implant
- Target vessel patency, patient level, annually from 2-5 years post-implant (extended primary endpoint)
- Target vessel patency, vessel level analysis, annually from procedure to 5 years post-implant

Secondary safety outcomes

- Aneurysm-related mortality at 12 months and annually through 5 years post-implant
- MAEs at 30 days

CONFIDENTIAL INFORMATION

4. Registry Population

4.1. Description of Population

The registry population will consist of patients that have had treatment with [REDACTED] and that meet the registry eligibility criteria.

Subject Cohort	Treatment period	FU period after index procedure* (years)	Number patients	Caps per site** (patient)
Fenestrated repair (FEVAR)	From July 2021 to Jan 2017	5	100	First cap 10% (10 patients) Second and max cap 30% (30 patients)
Branched repair (BEVAR)	From July 2021 to Jan 2017	5	120	First cap 10% (12 patients) Second and max cap 30% (36 patients)
Fenestrated-branched repair***	From July 2021 to Jan 2017	5	Up to 40	N.A.

* Subject who died before the end of FU period will be not excluded from the registry.

** for FEVAR and BEVAR cohorts an enrollment cap is fixed at 10% of the total patients without sponsor approval. With sponsor approval, a single site may enroll a maximum of 30% of total patients.

***Hypothesis testing will be performed on the FEVAR and BEVAR cohort only.

Target for hypothesis testing is to have 220 subjects among FEVAR and BEVAR only subjects. The registry also accounts for mixed cases that can be enrolled according to consecutive screening procedure, as described in section 5.5

Site's registry staff will review patients' medical records to identify eligible patients for this retrospective and prospective data collection. The registry has been designed with standard eligibility criteria to enroll subjects for which the registry device has been intended to treat. Only patients who meet all of the inclusion criteria and none of the exclusion criteria will be included in the registry.

Considering the nature of the patient's disease, elderly patients (≥ 65 years old) can represent the majority of subjects enrolled in this registry. This population can include patients with cognitive disorder or severe dementia.

According to EU regulation, elderly patients are considered vulnerable population. However, considering the retrospective nature of the registry, the patients have already been treated at the time of the inclusion, therefore there are not additional risks for this vulnerable population (please see risk assessment at (section 9) to be included in this registry).

CONFIDENTIAL INFORMATION

4.2. Inclusion Criteria

The Inclusion Criteria reflects the potential broad application of the device as evaluated by the medical judgement of the implanting physician. Inclusion Criteria will be evaluated at the time of initial identification as part of the retrospective device-use search using the patient health status at the time of the index procedure.

1. Patients treated with the [REDACTED] as a Bridging Stent in conjunction with a branched/fenestrated stent graft to allow endovascular aneurysm repair from 31 December 2021 until 01 January 2017
2. Age ≥ 18 years at the time of implant
3. Provision of informed consent by the patient or next of kin/legal representative (for deceased patients at registry entry, unless a waiver was granted), according to local regulations.

4.3. Exclusion Criteria

1. Patient treated for ruptured aneurysm or who were otherwise hemodynamically unstable at the time of the procedure
2. Patient treated for acute or sub-acute dissection, <90 days from onset of symptoms
3. Patient treated using physician-modified endovascular grafts
4. Patient intended to be treated with chimney, periscope, octopus, sandwich technique per the pre-treatment case plan
5. At the time of treatment, patient had known coagulation disorders including hypercoagulability that were not amenable to treatment
6. Patient was pregnant at the time of treatment.
7. Participation in another drug or device investigational study within one year of device implant, that can confound the registry endpoints.
8. Patient had known or suspected systemic infection (including treatment for mycotic aneurysm) at the time of implant.

5. Registry Procedures / Evaluations

No product or procedure-related training is required, the registry is designed to retrospectively collect pseudo-anonymized data on demographic (including medical history), procedure, clinical follow-up, and device characteristic from the patient's medical record.

Similarly, for follow-up data that will be collected prospectively, the registry will not require the use of any procedure and / or test and / or medical device different from those required by routine clinical practice for following up the investigated pathologies. Each site will be responsible for using and maintaining the equipment and medical devices in accordance with the manufacturer's directions and their institutional practices.

[figure not shown]
[figure not shown]
[figure not shown]
The sponsor will not impose requirements that limit health care professionals from exercising their best medical judgment for treatment. Therefore, follow-up modalities will be determined by physicians based on clinical practice standards.

For this registry it is expected that the sites will follow this protocol to ensure scientifically sound evaluation of outcomes. There are no additional, known or foreseeable factors that may compromise the outcome of the registry or the interpretation of results; please refer to section 3.3 regarding minimization of bias.

CONFIDENTIAL INFORMATION

5.1. Registry Procedures and Evaluation Schema

CONFIDENTIAL INFORMATION

[figure not shown]
MD133246 Protocol Template

Revision#: 7

Doc Type: GC

Page 11 of 37

5.2. Schedule of Events

¹ Available information used in case planning (e.g. diagrams, imaging) will be requested as part of registry documentation

² Available imaging performed per the site standard of care for complex EVAR procedures and follow-up. This may include angiography, echocardiography, X-Ray, computed tomography and/or magnetic resonance. Any available imaging performed (fully anonymized) can be requested as part of registry documentation.

³ Medication collected: Antiplatelet and anticoagulant therapy

⁴ The start of the prospective phase may change from subject to subject depending on the treatment date.

[figure not shown]
⁵ collection of any possible re-intervention data

⁶ Lab result will be collected if available, and can include, RBC, WBC, platelet, Creatinine, eGFR

5.3. Informed Consent Process

For the inclusion of patients in the registry, the investigator should review all inclusion/exclusion criteria and, in the case of including patients who are alive and reachable at the site, the patient will be required to sign the Ethics Committee approved Informed Consent Form (ICF) before enrolment in the registry.

As this registry is retrospective and considering the nature of patient's disease, some patients may [REDACTED]

If, during the course of the registry, patients who were not previously reachable come back to the clinical site for a visit, the investigator is expected to collect informed consent from those patients.

CONFIDENTIAL INFORMATION

To protect patient privacy, patient-identifiable information (e.g., name, initials, complete birth date, and race) will not be collected in the registry clinical data management system.

The informed consent form will include emergency contact details for any concerns. The case history (i.e., source documents / subject chart) for each subject shall document that such informed consent was obtained.

The EC approved consent form will be signed and personally dated by the subject or next of kin/legal representative (for deceased patients at registry entry, unless a waiver was granted), according to local regulations and the person who conducted the informed consent discussion. The original signed informed consent form will be retained in the subject records. A copy of the signed informed consent document will be given to the subject for their records.

5.3.1.

Considering the low risk (see section 8, Risk Assessment) of this retrospective registry and the absence of registry-specific procedures for the patient, the

Specific procedures to ensure adequate documentation of the informed consent process, in accordance with regulation and best clinical practice, will be provided to the investigators in a separate document.

5.3.2. Vulnerable Populations

Vulnerable population is described in section 4.1

In case the patient is unable to make the decision to participate in this registry, Informed consent should be signed by next of kin/legal representative (LAR), according to local regulations. In such cases, the subject shall also be informed about the registry within his/her ability to understand and the subject should sign and personally date the written informed consent if capable.

5.3.3. Emergent Cases

Not applicable due to retrospective nature of the registry

5.4. Pre-Screening

Site are expected to perform a search of patients treated with [REDACTED] as a Bridging Stent in conjunction with a branched/fenestrated stent-graft within the hospital database following the site initiation performed by Gore. Upon site activation, [REDACTED]

CONFIDENTIAL INFORMATION

Screening will be divided in two phases:

[REDACTED]

The research results will be recorded in the Pre-screening list based on patient's date of index procedure in reverse chronological order (from newest to oldest patient treated).

[REDACTED]

The pre-screening list produced during phase one and two must be maintained at the site in order to document the reasons for exclusion for any patient preventing bias of the data. This list cannot be sent to Gore/other external individuals (CRO) but is available at the site in the registry binder for audit/inspection purposes.

5.5. Enrollment

Patient enrollment should be consecutive, and will occur according to paragraph 5.4.

From the pre-screening list (sorted by treatment date), the site should review patients against inclusion and exclusion criteria, then check whether the patients are still alive and reachable in order to obtain consent. The patient is considered enrolled when informed consent is obtained [REDACTED] (LAR), according to local regulations

In order to minimize selection bias and to prove that patients have been screened in consecutive fashion, all patients, present in the pre-screening list, who will undergo inclusion/exclusion criteria assessment, [REDACTED] until the site reaches the max cap of enrolled patients planned for this registry or until the cohort is completed.

If patient identified in the pre-screening list will not be enrolled, [REDACTED]

[REDACTED] no personal information is recorded. The investigators will identify additional subjects to be screened.

During the on-site monitoring visit, the monitor should review Subject Screening and Enrollment log against the subjects recorded in the EDC, in order to prove the enrolment occurred sequentially.

5.6. Screening

Formal screening will not be performed due to retrospective nature of this registry.

No screening procedures are performed, with exception of reviewing of the inclusion and exclusion criteria based on the information already present in the patient's medical record.

5.7. Screen Failure

For clarity, this registry defines screening failure as subjects from the pre-screening list who:

- do not meet Inclusion/Exclusion criteria.
- declined consent.

However, if after the collection of the consent, the subjects do not meet eligibility criteria, the primary reason for screen failure [REDACTED].

The subject will be excluded from the registry and a replacement subject may be enrolled in agreement with sponsor and investigator.

CONFIDENTIAL INFORMATION

5.8. Randomization and or Blinding

No randomization or blinding is to be performed due to the confirmatory nature of the registry design.

5.9. Procedure

The registry procedures consist of two phases, retrospective phase and prospective phase. The retrospective phase consists only of the collection of retrospective data (baseline, treatment and FU data) from the source documents available at the site from the time of the treatment until the enrollment date (ICF signature). It is expected that sites will provide pre and post treatment as well as treatment images for Core Lab review.

The prospective phase consists in collection of follow-up visits from the enrollment up to 5 years. The FU data collected prospectively can change from subject to subject depending on the index procedure date. Diagnostic imaging, treatment interventions, and follow up will be determined by physicians based on clinical practice standards.

5.10. Repeat Interventions

Reinterventions may be performed at the discretion of the principal investigator / sub-investigator to treat AEs. Any reinterventions performed will be documented on the CRF form. The components used as part of the reintervention, the date of the reintervention and the AEs leading to reintervention will also be documented on the CRF form.

5.11. Follow Up

All follow-up performed from the index procedure to the ICF signature will be collected retrospectively. FU data will be collected from the information already present in the medical chart.

From the date of the enrollment, all FU visits including any imaging, performed according to hospital standard of care, will be collected up to 5 years post index procedure.

In addition to in person visits, remote phone follow-up is also acceptable and clinical information obtained via phone can be collected.

For testing done at institutions different than the registry site, or in case no follow-up data are available, investigators should make any efforts to retrieve documentation from the patient or from other records/sources (e.g. hospital databases, family doctor, family members).

Subjects will continue to be followed by the site's standard of care after completion of the registry.

5.12. Subject Withdrawal from the Registry

A subject may withdraw from the registry at any time and should notify the investigator in this event. The investigator may also withdraw the subject from the registry at any time based on his / her medical judgment. The sponsor may retain and continue to use any data collected before the withdrawal of consent, if not explicitly requested otherwise by the subject.

If such withdrawal is due to problems related to the device safety or performance, the investigator shall ask for the subject's permission to follow his / her status / condition outside the registry.

CONFIDENTIAL INFORMATION

During the prospective phase, patients may be considered withdrawn for any of the following:

- Death
- Voluntary withdrawal
- Investigator withdrawal
- Any other medical condition where evaluation of the [REDACTED] is not feasible (e.g., bypassed [REDACTED], explant of the device)

If the discontinuation is caused by the development or worsening of AEs, information on the AEs must also be recorded on the appropriate eCRF. All data generated prior to patient withdrawal will be maintained, and registry data will be used as appropriate.

If possible, an additional evaluation of the [REDACTED] (s) is recommended prior to their withdrawal from the registry.

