Reintervention	
Any repeated vascular or nonvascular procedure related to the index procedure
 
Reintervention will be adjudicated as major or minor based on the following
 
Major: deployment of proximal or distal aortic or iliac extensions, removal of the device, use of thrombectomy or thrombolysis, and any major open surgical procedure.
 
Minor: endovascular procedures (percutaneous transluminal angioplasty, atherectomy, stenting) without thrombectomy or thrombolysis, interventions to treat branch vessel stenosis, interventions to treat type II endoleak or branch-related endoleaks, and minor surgical revisions (patch angioplasty) of the access vessels.
 
Each reintervention will be adjudicated as related to a [REDACTED]-treated branch vessel component, related to a non-[REDACTED]-treated branch vessel component, or related to main body component(s), if possible.

Target vessel instability	Death or rupture related to side branch complication (e.g., endoleak) or reintervention to treat a branch-related complication, including endoleak, disconnection, kink, stenosis, occlusion, or rupture

CONFIDENTIAL INFORMATION

Aneurysm-related mortality	Any death that occurs within the first 30 days or any death that results from aneurysm rupture, aorta-related complications (eg, infection, occlusion, dissection, hematoma), or a complication of a secondary intervention
Major Adverse Events (MAEs)	
All-cause mortality
 
Myocardial infarction (MI): MI resulting in severe hemodynamic dysfunction necessitating resuscitation, cardiac arrest, or fatal outcome.
 
Respiratory failure requiring prolonged (>24 hours from anticipated) mechanical ventilation or reintubation
 
Any renal function deterioration according to the RIFLE classification system.
 
Bowel ischemia requiring surgical resection or not resolving with medical therapy
 
Permanent paraplegia (any grade 3 A-C spinal cord injury) in a patient who is no ambulatory.
 
Any major stroke defined according to National Institutes of Health Stroke Scale (NIHSS) or equivalent.

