5.15. Explant Procedures

The [REDACTED] may be explanted during a surgical procedure or as part of an autopsy. If this occurs during the prospective phase of the registry sites are requested to return explanted devices to the sponsor for gross and histological evaluation. Prior to planned or potential device retrieval, contact the Gore Associate managing the registry to communicate that a specimen is being retrieved from a registry subject. A specimen shipping kit will be immediately sent to the site. The specimen kit provides specific packaging and handling instructions for the specimen and contains a shipping container.

In complex aortic procedures it is expected that more than one [REDACTED] can be implanted in the same subject, if the explanted device is the only one used in the subject then the subject will be discontinued, if other [REDACTED] remain implanted the subject will continue in the registry.

6. Registry Administration

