9.1.3. Adverse Event Reporting and Coding

Adverse event reporting begins after enrolment, starting from index procedure date, and ends when the subject completes the 5 years visit. After enrollment all adverse events from the retrospective phase will be reported by the site in the EDC with the initial data entry. Adverse events that occur in the prospective phase will be reported as soon as possible.

For any condition reported in the medical history and / or present at baseline or index procedure do not report as an adverse event unless it becomes serious or increase in intensity, or if a worsening of a baseline condition is reported.

AEs will be reported on the appropriate CRF and documented in the subject's permanent medical record. The investigator at each site is ultimately responsible for reporting AEs to the sponsor.

The following information on each reported AE will be collected:

- Adverse event name
- Adverse event onset date
- Relationship
- Classification serious or non-serious
- Treatment

CONFIDENTIAL INFORMATION

- Outcome
- Resolution date

Adverse events will be coded using the Medical Dictionary for Regulatory Activities (MedDRA).

Adverse event submission guidelines:

- Adverse event reporting begins once the patient is enrolled in the registry. All adverse events should be reported from enrollment through registry completion / discontinuation.
- Provide a diagnosis if possible. If unable to provide a diagnosis, report the symptoms as separate events. Adverse events should be reported using the full name without abbreviations or narratives.
- Adverse events with an outcome status of “ongoing” should be assessed at each follow-up evaluation to determine if the event has resolved. Adverse events ongoing at registry completion / discontinuation should be left as “ongoing” on the AE case report form.

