9.1.4. Subject Death

In this registry, death is not considered an AE, but rather the outcome of an AE. An ongoing AE at the time of death or registry withdrawal will remain categorized as ongoing.

Attempts will be made by the Site to obtain death certificate and autopsy reports, when possible.

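### After a prospective-phase withdrawal for bypass of a study stent, or explant of the only one, later aneurysm- or branch-related deaths and reinterventions have no stated route into the five-year data

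*Protocol*

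**What the plan says.** Protocol 5.12 lists grounds on which a patient may be considered withdrawn during the prospective phase. One is "Any other medical condition where evaluation of the [REDACTED] is not feasible (e.g., bypassed [REDACTED], explant of the device". The wording is permissive and does not extend to the retrospective phase. If a withdrawal is due to device safety or performance, the investigator asks for "permission to follow his / her status / condition outside the registry". Data generated before withdrawal are kept.

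Protocol 5.15 is firmer, but covers explant only: "if the explanted device is the only one used in the subject then the subject will be discontinued", whereas "if other [REDACTED] remain implanted the subject will continue in the registry". It expects that a patient may have more than one study stent. It does not mention bypass.

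Protocol 9.1.3 gives two end points for adverse event reporting. One sentence ends it at the five-year visit. The submission guidelines say: "All adverse events should be reported from enrollment through registry completion / discontinuation". "Adverse events ongoing at registry completion / discontinuation should be left as" ongoing, so their final outcome is not sought.

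Protocol 9.1.4 says of deaths: "Attempts will be made by the Site to obtain death certificate and autopsy reports, when possible".

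Protocol 3.4.3 reports aneurysm-related mortality, target vessel instability and reintervention at 12 months and then yearly to year 5. Under 3.4.1, target vessel instability means "Death or rupture related to side branch complication (e.g., endoleak) or reintervention to treat a branch-related complication". Protocol 10.4.6 says missing secondary-endpoint data are not imputed; the rest of that method is redacted.

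**The concern.** These rules tie two different things together: the end of device evaluation and the end of registry data collection. A stent that has been bypassed or removed can no longer be assessed for patency. The patient can still die of an aneurysm-related cause, or need another procedure.

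The definitions in 3.4.1 make this matter. They class taking out the device and major open surgery as major reinterventions. They count a death from a complication of a secondary intervention as aneurysm-related. Collection may therefore stop just as the patient becomes exposed to an event that the endpoint is meant to count.

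At stake is late safety, which is the registry's secondary objective. The patients dropped are selected by device failure, so their later risk may differ from that of the others. No analysis can recover deaths that were never collected.

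**Working it through.** **Step 1. Follow the patient through the text.**

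| Situation | Governing text | Collection to year 5 |
|---|---|---|
| Bypass or explant before consent | 5.11: chart data from index procedure to consent are collected | Not stopped by the 5.12 ground, which is prospective only |
| Prospective explant, other study stents remain | 5.15: patient continues | Continues |
| Prospective explant of the only study stent used | 5.15: patient is discontinued | Ends |
| Prospective bypass, other study stents remain or not | 5.12: may be considered withdrawn; 5.15 silent | May end |

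The gap lies in the last two rows.

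**Step 2. Look for a route into the data after withdrawal.**
- 5.12 places later follow-up outside the registry and names no link to the database or endpoints.
- 9.1.3 stops adverse event reporting at discontinuation in one sentence. The sentence naming the five-year visit does not help directly, because a discontinued patient has no such visit in the registry.
- 9.1.4 and the general record-retrieval instruction in 5.11 do not address withdrawn patients.
- 11.7 points to section 5.2 for individual termination procedures. The visible part of 5.2 is a set of schedule footnotes, and none covers this.

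No route is visible.

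**Step 3. Size.** The plan states no rate of bypass, explant or late death, so there is no figure to reproduce. Every rate below is an assumption.

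Inputs:
- N = 100 + 120 + 40 = 260 (Protocol 4.1, with the mixed cohort at its maximum).
- Aneurysm-related death in the other patients: 3% (assumed).
- k = 3, 8 or 13 patients who would be stopped if the rule covered all five years (assumed).
- q = 3%, 10% or 20% later aneurysm-related death in stopped patients (assumed).
- f = share of the five years that is prospective = mean of max(0, 5 − (E − T))/5, for treatment date T and consent date E. Consent is assumed at the start of 2022, 2023 or 2024:
  - T uniform from 1 January 2017 to 31 December 2021 (4.2): f = 0.50, 0.32, 0.18.
  - T uniform over the last two years of that window, as newest-first screening (5.4) could produce: f = 0.80, 0.60, 0.40.
  - T uniform from January 2017 to mid-2021, since the table in 4.1 says July 2021: f = 0.45, 0.27, 0.14.

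Range used: f = 0.2, 0.5, 0.8.

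Formulas: stopped = f·k; missed deaths = f·k·q; understatement = f·k·(q − 0.03)/260 if stopped patients leave the denominator, or f·k·q/260 if they stay in as event-free.

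| Case | f, k, q | Stopped | Missed deaths | True rate | Observed (left out / event-free) | Understatement, points |
|---|---|---|---|---|---|---|
| Low | 0.2, 3, 3% | 0.6 | 0.018 | 3.00% | 3.00% / 2.993% | 0 / 0.007 |
| Mid | 0.5, 8, 10% | 4 | 0.40 | 3.108% | 3.00% / 2.954% | 0.108 / 0.154 |
| High | 0.8, 13, 20% | 10.4 | 2.08 | 3.68% | 3.00% / 2.88% | 0.68 / 0.80 |

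Mid case in full: true = (256 × 0.03 + 4 × 0.10)/260 = 8.08/260 = 3.108%; event-free = 7.68/260 = 2.954%.

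Over all 27 combinations, the event-free gap is below 0.5 points in 25 (the others are 0.50 and 0.80), with median 0.10. The left-out gap is below 0.5 in 26, with median 0.06. Lowering f to 0.14 moves only the bottom of the range: 0.14 × 3 × 0.03 = 0.013 missed deaths.

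These figures lean high. Withdrawal under 5.12 is optional, explant patients with other study stents continue, and a prospective-phase stop leaves less than five years in which to miss events. If stopped patients have the same risk as the rest and leave the denominator, there is no bias.

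**The case against.** The strongest case against has four parts.

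*The effect is small.* At 3% and N = 260 the standard error is √(0.03 × 0.97/260) = 1.06 points, or 1.71 and 1.56 points in cohorts of 100 and 120. Even the high case is below one standard error. This stands, and it limits how much weight the point can carry.

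*The device is the subject of the registry.* Stopping when no study stent can be assessed is a defensible choice. 5.10 and 5.12 record the reintervention and the adverse event behind a discontinuation. This supports ending patency assessment. It does not support ending the count of deaths in endpoints reported to year 5.

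*Some text is not visible.* The schedule table, the evaluation schema and the secondary analysis methods cannot be read. This stands as a limit: the finding is about the visible text, and the censoring rule cannot be judged.

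*General provisions may cover the gap.* 9.1.4 and 5.11 do not exclude withdrawn patients. They do not include them either, and 5.12 and 5.15 are the specific rules.

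A reader might also infer more than the documents support:
- That any explant ends collection. 5.15 keeps patients who have other study stents.
- That adverse event reporting certainly stops at withdrawal. 9.1.3 gives two end points.
- That deaths in general go uncollected. Death is itself a withdrawal reason in 5.12, and certificates are sought.
- That 5.12 and 5.15 flatly conflict. They can be read together, except that bypass has no per-stent rule.
- That the primary endpoint is exposed. SAP 5.0 counts loss of patency before 15 months as failure whatever later visits exist.

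**Conclusion.** The concern holds in a narrow form. It is confined to prospective-phase withdrawal after bypass of a study stent, or after explant of the only one used. For these patients the visible text gives no way for an aneurysm-related death, branch-related death or reintervention before year 5 to reach the registry data. The loss may be informative and would tend to understate late aneurysm-related mortality if these patients are at higher risk.

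The size is unknown and probably small: a few tenths of a point at most in nearly all the combinations tried. That rests on assumed withdrawal counts, death risks and consent dates, with uniform treatment dates. The change is worth making because it is cheap and the data cannot be recovered later, not because it is likely to overturn a conclusion.

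**What to change.** - In Protocol 5.12 and 5.15, separate the end of device or patency evaluation from the end of registry data collection, and align the two sections. State how bypass is handled when other study stents remain.
- After bypass or sole-device explant, subject to consent, keep collecting vital status, cause of death, reintervention and the status of other treated vessels to year 5. Use standard-of-care records or phone contact, which 5.11 already allows.
- In 9.1.3, reconcile the two end points for adverse event reporting, and allow the outcome of an event open at that time to be updated.

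The cost is a wording amendment and a few extra record or phone checks in a small number of patients. It adds no procedure and changes no clinical management.
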